3.7. STUDY PROCEDURES AND FLOWCHART

An overview of the study design is shown in Figure 1. Study assessments will be performed at the visits and time points outlined in the Time and Events Schedule (Table 2).

Figure 1 Study Schematic

DRC=data review committee; ER=extended release; HCl=hydrochloride; IV=intravenous; MSD=maximum safe dose.

At each dosing of active drug, the dose will be added to a flavored beverage to prepare a dosing volume of 150 mL. An additional 50 mL of a flavored beverage will be added as a rinse to the empty dosing container that contained the 150 mL solution and then administered to the subjects.

At least 12 hours after completing the naloxone challenge, eligible subjects will receive a single oral dose of nalbuphine HCl solution or placebo solution in a randomized, double-blind manner. Each cohort will comprise 8 unique subjects who will be randomized to nalbuphine HCl (n=6) or placebo (n=2).

Following completion of each cohort, safety data will be unblinded and reviewed by the DRC. Escalation to the next dose level will continue until the MSD is identified. Dose reductions and intermediate doses may be considered based on the results obtained in previous cohort(s). Additional cohorts of subjects may be added until the MSD is identified, or if additional data are required at a given dose level or at a dose intermediate to those specified, or a dose higher than those planned is required to be tested, based on supportive safety data. If a dose higher than planned will be tested, the dose to be administered will be up to 50% greater than the dose administered in the previous cohort, based on supporting safety data..

Table 2 Time and Events Schedule

	Screening Visit	Dose Selection Phase															
		Naloxone Challenge	Dose Selection Cohorts														
Visit:	1		2														
Day:	-30 to -2	-1	1													2	
Assessment time points relative to dosing (hours)																	
Subject Review																	
Informed Consent	X																
Medical History	X	X ^a															
Medication and Recreational Drug and Alcohol Use History	X																
Inclusion/Exclusion	X																
Inclusion/Exclusion Eligibility		X															
Study Restrictions Review		X															
Demographics	X																
DSM-IV-TR	X																
C-SSRS (Baseline version)	X																
Safety																	
Physical Examination	X	X ^b														X ^b	
Height, Weight, BMI	X																
Serum Pregnancy	X	X															
Urine Pregnancy		X															
FSH (postmenopausal women)	X																
HIV, Hepatitis B, Hepatitis C	X																

^a Focusing on any changes since the last visit.

^b Symptom-directed physical examination

	Screening Visit	Dose Selection Phase																			
		Naloxone Challenge	Dose Selection Cohorts																		
Visit:	1	2																			
Day:	-30 to -2	-1	1													2					
Assessment time points relative to dosing (hours)																					
			Pre				1		2		3	4	5	6		7	8	10	12	24	
Vital Signs ^c	X	X ^d																			24
Oral Temperature	X	X																			24
Electrocardiogram	X	X																			24
Urine Drug Screen	X	X																			
Breath Alcohol	X	X																			
Continuous Pulse Oximetry ^e			Predose until at least 6 hours post-dose																		
Clinical Laboratory Tests	X																				24
Concomitant Medications			< -- recorded throughout -- >																		
Adverse Event Monitoring ^f	X	X	< -- recorded throughout -- >																		
COWS		X																			
Pharmacokinetics																					
Nalbuphine			Pre	0.25	0.5	1	1.5	2	2.5	3	4	5	6			8	10	12	24		
Pharmacodynamics																					
Pupillometry			Pre	0.25	0.5	1	1.5	2	2.5	3	4	5	6			8	10	12	24		
Study Administration																					
Naloxone Administration		X ^g																			
Randomization			pre ^h																		
Admission		X																			

^c Vital signs will include blood pressure, heartrate, and respiratory rate. Vital signs will also include measurements of oxygen saturation after continuous pulse oximetry monitoring is complete.

^d Pre-naloxone challenge and at 10 minutes and 1 hour post-naloxone challenge, as indicated in Section 4.4 of the Protocol.

^e Oxygen saturation will be monitored continuously via telemetry for at least 6 hours post-dose or longer, if deemed necessary by the investigator or designee to ensure subject safety.

^f Spontaneous AE reporting is continuous throughout the study; however, AE questioning may be performed using a non-leading question at discretion of the clinical staff.

^g Naloxone challenge procedures are described in Section 4.4 of the Protocol. For female subjects, the results of the urine pregnancy test are required prior to the naloxone challenge; results of the serum pregnancy test will not be required prior to the naloxone challenge.

^h Day 1 only.

	Screening Visit	Dose Selection Phase													
		Naloxone Challenge	Dose Selection Cohorts												
Visit:	1	2													
Day:	-30 to -2	-1	1											2	
Assessment time points relative to dosing (hours)															
Study Drug Administration				0											
Discharge ⁱ															X

ⁱ Subjects will be discharged after assessments on Day 2 are complete and at the discretion of the investigator or designee to ensure subject safety.

4. ENDPOINTS

4.1.1. Pharmacokinetic Endpoints

The PK parameters that will be evaluated for nalbuphine, as applicable, include:

- C_{max} : maximum observed plasma concentration
- t_{max} : time to maximum observed plasma concentration
- AUC_{last} : area under the plasma concentration versus time curve from time 0 to the last measurable concentration

The following parameters will be derived for nalbuphine if sufficient data are available:

- AUC_{inf} : area under the plasma concentration versus time curve extrapolated to infinity
- k_{el} : first-order elimination rate constant associated with the terminal (log-linear) portion of the curve
- $t_{1/2}$: apparent first-order terminal elimination half-life will be calculated as $0.693/k_{el}$
- CL/F : apparent clearance
- Vd/F : apparent volume of distribution

4.1.2. Safety Endpoints

The safety endpoints will include the following:

- Type, incidence, and severity of adverse events (AEs)
- Vital signs (blood pressure, respiratory rate, heart rate, oxygen saturation [SpO_2], and oral temperature)
- ECGs (heart rate and the PR, QRS, QT, QTcB, and QTcF intervals)
- Clinical laboratory tests (hematology, clinical chemistry, urinalysis)
- Physical examination findings

4.1.3. Exploratory Endpoints

The exploratory endpoints for this study are:

- Identification of a MSD of nalbuphine administered as nalbuphine oral solution.

- Concentration-versus-time profiles of nalbuphine in plasma and PK parameters C_{\max} , t_{\max} , and AUC_{last} . If data allow then the PK parameters AUC_{inf} , k_{el} , $t_{1/2}$, CL/F and Vd/F will be calculated.
- Pupillometry (maximum pupil constriction [MPC], time to MPC [TMPC], and time-averaged pupillometry area over the curve [TA_PAOC]).

5. CHANGE FROM ANALYSIS PLANNED IN PROTOCOL

Due to the unexpected closure of the investigational site prior to the initiation of Part B of this study, only Part A was completed. Part B will be placed with a new investigation site sometime in the future. As a result, only those endpoints associated with Part A will be summarized and evaluated. Consequently, this updated SAP provides a detailed description of planned assessments for Part A only.

6. ANALYSIS POPULATIONS

The study analysis populations will consist of the following:

- Dose Selection Randomized Population
- Dose Selection Safety Population
- Dose Selection PK Population

Details of subject evaluability criteria will be determined prior to study unblinding.

6.1. DOSE SELECTION RANDOMIZED POPULATION

The Dose Selection Randomized Population will include all subjects who are assigned a randomization number in the Dose Selection Phase. Unless specified otherwise, this population will be used for subject listings and for summaries of subject disposition for this phase.

6.2. DOSE SELECTION SAFETY POPULATION

The Dose Selection Safety Population will include all subjects in the Dose Selection Randomized Population who receive any Dose Selection treatment. The Dose Selection Safety Population will be used for all analyses of safety endpoints, the listing of PK concentration data and for the analyses of PD pupillometry data in this phase.

6.3. DOSE SELECTION PK POPULATION

The Dose Selection PK Population will include all subjects in Dose Selection Randomized Population who receive a dose of nalbuphine and have evaluable PK data, and who have no protocol deviations or other circumstances that would exclude them from analysis. Details of subject inclusion in the Dose Selection PK Population will be determined prior to study unblinding. The Dose Selection PK Population will be used for all PK analyses and for the listing of derived PK parameters in this phase.

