## 8. DATA ANALYSIS AND STATISTICAL CONSIDERATIONS

### 8.1 Statistical and Analytical Plans

#### 8.1.1 Analysis Populations

##### 8.1.1.1 Dose Selection Phase (Part A)

The following analysis populations will be used for Part A:

- *Dose Selection Randomized Population*: All subjects who are assigned a randomization number in the Dose Selection Phase.
- *Dose Selection Safety Population*: All subjects in the Dose Selection Randomized Population who receive any Dose Selection treatment. These subjects will be included in the safety analysis for this phase.
- *Dose Selection PK Population*: All subjects in the Dose Selection Randomized population who received a dose of nalbuphine and have evaluable PK data. These subjects will be used in the PK analysis for this phase.

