##### 8.1.1.2 Qualification and Treatment Phase (Part B)

- *Qualification Safety Population*: All subjects who receive at least one dose of study medication during the Qualification Phase.
- *Randomized Population*: All subjects who are assigned a randomization number in the Treatment Phase.
- *Safety Population*: All randomized subjects who receive any study treatment in the Treatment Phase.

- *Completers Population:* All subjects in the Safety population who receive all study treatments and complete all treatment periods in the Treatment Phase regardless whether they have protocol deviations. Subjects must have at least one response on Drug Liking VAS within 2 hours of  $T_{max}$  for each treatment in the study.
- *PK Population:* All subjects in the Randomized population who receive at least 1 dose of nalbuphine from whom at least 1 PK sample is obtained after dosing, and who have no protocol deviations or other circumstances that would exclude the subjects from analysis.

Details of subject evaluability criteria will be determined prior to study unblinding.

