### 8.1.2 General Statistical Considerations

Complete details of the statistical analyses to be performed by INC Research will be documented in a statistical analysis plan (SAP), which will be completed prior to unblinding of the study data. This document will include more detail of the analysis populations, summary strategies, and of any amendments to the proposed analyses listed here, if necessary. Any changes to the SAP will be outlined in the final clinical study report (CSR).

The PK analyses will be performed by INC Research using Phoenix WinNonlin (release 6.4 or higher) and other statistical analyses will be performed using SAS® (release 9.3 or higher).

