#### 8.1.4 Analysis of Pharmacokinetics

Pharmacokinetic analyses will be performed using the Dose Selection PK population in Part A and the PK population in Part B.

The PK parameters for plasma nalbuphine and (Part A only) its metabolites will be calculated using non-compartmental analysis and will be summarized by dose level in Part A and by treatment in Part B. Graphs of the concentration (original and log transformed) versus time will be generated. Descriptive statistics, including n, mean, SD, coefficient of variation (CV), minimum, median, and maximum will be calculated by dose level (Part A) and treatment (Part B) and time point for each study drug. Concentrations below the limit of quantification (BLQ) will be set to zero for the generation of summary statistics for concentrations and the generation of mean concentration-time plots.

For the calculation of the PK parameters, concentration-time data will be treated as follows: BLQ concentrations before the first quantifiable concentration will be set to zero; BLQ concentrations after the first quantifiable concentration will be treated as missing; and pre-dose sampling times relative to dosing will be set to zero. Descriptive statistics, including n, mean, SD, geometric mean, geometric CV, minimum, median, and maximum, will be calculated by dose level and treatment group for all PK parameters except  $T_{max}$ ,  $t_{1/2}$ , and kel. Time to maximum observed plasma concentration data will be summarized with minimum, median, maximum, Q1 and Q3. The  $t_{1/2}$  and kel data will be summarized with n, mean, SD, CV, minimum, median, and maximum.

PK profiles will be analyzed for all subjects, even if some PK sampling time points are missed. The PK parameters will be subject to quality control criteria. If quality control criteria are met, the PK parameters will be used in analyses and models. Quality control criteria for PK will be sufficient to eliminate unreliable data. Details will be provided in the SAP.

The PK parameters summary will be presented separately for a subset (if applicable) of subjects who do not vomit within 12 hours of dosing in Part A and Part B of the study.

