10.3. DERIVED AND IMPUTED DATA

- PK parameters (C_{max} , t_{max} , AUC_{last} , AUC_{inf} , $t_{1/2}$, k_{el} , CL/F and Vd/F) will be determined for nalbuphine and its metabolites based on concentrations in plasma and actual sampling times via non-compartmental analysis using validated Phoenix WinNonlin Version 6.4 or higher. For each subject, the PK parameters will be derived as follows: The apparent C_{max} and the corresponding t_{max} will be read directly from the concentration-time plot (observed data, not predicted data by the program);
- AUC_{last} and AUC_{inf} will be calculated using the linear up log down trapezoidal method;
- The elimination rate constant (k_{el}) will be determined by log-linear regression obtained on at least the three last quantifiable concentrations;
- The Terminal elimination half-life ($t_{1/2}$) will be calculated as $0.693/k_{el}$.
- AUC_{inf} is calculated by the program as:
 $AUC_{inf} = AUC_{last} + AUC_{t-inf}$ where t is the sampling time point of the last measurable concentration (t_{last}). AUC_{t-inf} is calculated by the program as: C_{last}/k_{el} , where C_{last} is the last measurable concentration at time t and k_{el} is the elimination rate constant during the terminal elimination phase;
- CL/F will be derived by $Dose/AUC_{inf}$ and Vd/F will be derived as CL/F divided by k_{el} .

The following reliability criteria will be used for the PK parameters:

- The adjusted square of the correlation coefficient (Rsquare adj.) for the goodness of fit of the regression line through the data points must be at least 0.80 for the k_{el} value to be considered reliable;
- The AUC extrapolation to infinity (AUC_{t-inf}) must be $\leq 20\%$ of the total area for AUC_{inf} to be considered reliable;

For subjects with unreliable k_{el} (e.g. Rsquare adjusted ≤ 0.80), k_{el} , $t_{1/2}$ and AUC_{inf} will be flagged in the individual data Listings. For subjects with unreliable AUC_{inf} (because of extrapolation $>20\%$), AUC_{inf} , CL/F and Vd/F will be flagged in the individual data Listings. Flagged PK parameters will be excluded from summarization and statistical analyses.

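### Does the deviation clause that the SAP adds to the Part A PK population need to be removed or spelled out?

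*SAP*

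**What the plan says.** Protocol 8.1.1.1 gives the Part A PK population as "All subjects in the Dose Selection Randomized population who received a dose of nalbuphine and have evaluable PK data". It does not define evaluable. In Protocol 8.1.1.2, the Part B PK population carries a further condition: subjects "who have no protocol deviations or other circumstances that would exclude the subjects from analysis".

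SAP 6.3 repeats the Part A definition and adds almost the same condition: "and who have no protocol deviations or other circumstances that would exclude them from analysis". It lists no deviations or circumstances, and continues: "Details of subject inclusion in the Dose Selection PK Population will be determined prior to study unblinding". SAP Section 5, which reports departures from the protocol, covers only the loss of Part B: "Consequently, this updated SAP provides a detailed description of planned assessments for Part A only".

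Two protocol sections bear on how much the SAP may settle. On the SAP, Protocol 8.1.2 says: "This document will include more detail of the analysis populations, summary strategies, and of any amendments to the proposed analyses listed here". Protocol 8.1.4 says: "Quality control criteria for PK will be sufficient to eliminate unreliable data. Details will be provided in the SAP".

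On blinding, Protocol 5.5.1 and SAP 3.5 break the codes after each cohort. Protocol 4.9.1 puts a sponsor representative and the investigator or a designee on the Data Review Committee (DRC), which sees unblinded safety data and, if available, PK data. SAP 6.4 has the sponsor, principal investigator, lead statistician and study scientist review deviations and finalise them before unblinding.

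**The concern.** Three things look wrong together. A subject-level exclusion has moved from Part B into Part A without an entry in the SAP section meant to record such changes. The exclusion has no stated criteria, and the reliability rules in SAP 10.3 cover k_el, AUCinf and the parameters flagged with them, not Cmax or AUClast. The safeguard offered is a decision before unblinding, yet in Part A the sponsor and investigator roles that review deviations also sit on the committee that has seen each cohort unblinded. SAP 2.1 and Section 5 show that this SAP was written after Part A had finished.

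If a reviewer had seen individual concentrations, an open-ended clause could let an inconvenient profile be dropped. With six active subjects per dose, one removal takes out 1/6 = 16.7% of a dose level. PK is a Part A objective, and Protocol 4.9.2 allows an exposure plateau to help identify the maximum safe dose, so the PK summaries deserve protection.

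**Working it through.** The plan gives no figure for this point, so the check is a comparison of text followed by an illustration of scale.

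**Text**

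1. *How large is the change?* The protocol already restricts the population to evaluable PK data without defining the term, so judgement about unusable profiles was there before the SAP. The added clause does not remove everyone with a deviation, only those whose deviation would exclude them. It can fairly be read as a gloss on evaluable.
2. *Was the SAP entitled to make it?* Yes. Protocol 8.1.2 foresees population detail and amendments in the SAP, and 8.1.4 leaves PK quality control to it. What is missing is a line in Section 5.
3. *Are Cmax and AUClast without any rules?* No. SAP 10.4 handles values below quantification, missing sampling times and profiles with no quantifiable sample. SAP 10.5 (and Protocol 8.1.4) gives a separate parameter summary for subjects who do not vomit within 12 hours, an obvious threat to these parameters after an oral solution. SAP 10.3 adds: "Flagged PK parameters will be excluded from summarization and statistical analyses". Each subject takes one supervised dose (Protocol 5.2.7 and 5.6), so there is little room for dosing deviations.
4. *Which unblinding is meant?* The SAP does not say. SAP 2.2 places the analysis after database lock, so study unblinding can naturally mean the final one, as distinct from the cohort code breaks.
5. *Can knowledge of the arm bias a PK exclusion?* Not by itself. Every candidate for this population received nalbuphine at a known dose. Bias would need someone to see individual concentrations (or correlated safety or pupil data) and then use them in the deviation review. Protocol 6.2 withholds potentially unblinding concentrations from the site and blinded staff. The documents do not show what the committee saw.
6. *Could a removal be hidden?* No. SAP 6.4 lists all deviations, SAP 8.1 and Listing 16.2.3.3 list excluded subjects, and Listing 16.2.6.2.1 gives sample collection data and concentrations for the whole Safety Population.

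**Scale**

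Inputs: 6 nalbuphine subjects per cohort (Protocol 3.1.2), and inter-subject variability of 54% for Cmax and 46% for AUC (Protocol 12.2). Assumption: these percentages are coefficients of variation (CV).

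- Removing one value 1 SD above the mean of 6 lowers the mean by CV/5. Cmax: 0.54/5 = 10.8%. AUC: 0.46/5 = 9.2%.
- Standard error of a cohort mean, CV/√6. Cmax: 0.54/√6 = 22.0%. AUC: 0.46/√6 = 18.8%.
- A proportional 1.5-fold step in Cmax would read 1.5 × 0.892 = 1.34 if that subject is lost from the higher cohort, or 1.5/0.892 = 1.68 if from the lower. The standard error of a ratio of two cohort means is about 0.54 × √(2/6) = 31.2%.
- Deliberate worst case, always dropping the highest of six: log SD = √ln(1 + CV²) = 0.506 for Cmax and 0.438 for AUC. Simulating 400,000 lognormal samples of six, the arithmetic mean falls on average by 14.9% for Cmax (5th to 95th percentile 5.8% to 28.9%) and 12.7% for AUC. If 54% is instead a log-scale SD, the Cmax figure is 16.0%.
- Geometric means, which the SAP also reports: the expected largest of 6 standard normals is 1.2675, so the ratio is exp(−0.506 × 1.2675/5) = 0.88 for Cmax and exp(−0.438 × 1.2675/5) = 0.895 for AUC.

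**The case for a change.** The best case for a change is that it costs little and the text is plainly loose. Permission to amend in the SAP is not permission to leave the amendment unreported, and Section 5 exists for that purpose. Amendment 2 already describes results in drug-treated subjects by dose for the first four cohorts, so for Part A a decision before unblinding cannot mean before any code was broken. Derived PK parameters are listed only for the PK population, so an excluded subject's Cmax and AUClast would appear in neither the table nor that listing. No all-dosed table is planned.

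Most of this stands as description: the Section 5 omission is real, the criteria are not written down, and the unblinding is not defined. The traceability point goes less far. Cmax can be read from the listed concentrations, and AUClast rebuilt from them with the formula in SAP Appendix A, for at most six subjects per dose. The blinding point shows only that the safeguard is not assured for two roles. Those roles may be filled by different people, and the lead statistician and study scientist may have stayed blinded.

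The same worry about pupillometry is weaker. The discretionary exclusion in SAP 9.1.2 touches only by-time-point summaries. The three pupil endpoints lie outside it and use actual assessment times, and the SAP table index has only a pupillometry parameter table. SAP 3.5 reads as if PD data are always reviewed, but SAP 3.2 says only that they may be unblinded.

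**Conclusion.** No change follows. This is an unreported detail in an area the protocol leaves to the SAP, and analysts would fill it sensibly by excluding profiles that a deviation has made uninterpretable. Writing the criteria down, adding a line to Section 5 and naming the unblinding would be tidier, but no gain in the results is shown.

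The effect is confined to descriptive PK summaries with six active subjects per dose. A typical single exclusion moves a cohort mean by about 9% to 11%, and outcome-driven removal of the highest value by about 13% to 16% on average. Both are inside the 19% to 22% standard error of that mean, although the upper tail of the worst case for Cmax (28.9%) is not. A typical single exclusion leaves a proportional 1.5-fold step visible at 1.34. The SAP plans no test of proportionality or plateau, and the escalation decisions were the DRC's, taken while Part A ran, so the SAP population cannot alter them.

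This rests on two assumptions: that the 54% and 46% are coefficients of variation with roughly lognormal data, and that exclusions are few and made for documented reasons. The planned listings would let a reader test the second.
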